#### 4. STUDY DESIGN

## 4.1. Summary of Study Design

This is an open-label, non-randomized, Phase 2/3, multi-center study designed to evaluate the safety and diagnostic performance of F-DCFPyL PET/CT imaging to determine the presence or absence of metastatic prostate cancer in subjects with high risk prostate cancer who were planned for radical prostatectomy with pelvic lymph node dissection (cohort A), and subjects with radiologic evidence of local recurrence or new or progressive metastatic disease (cohort B) who were biopsied if a positive lesion was found on the F-DCFPyL PET/CT scan. The physician has the option to change the planned protocol specified procedure (i.e., RP ePLND for Cohort A subjects and Biopsy for Cohort B subjects) for the subjects based on the F-DCFPyL PET/CT scan. The details of these changes will be collected on the CRF, and these subjects obviating the planned procedure will not be included in any of the primary or secondary endpoints.

Eligible subjects will be enrolled in a non-randomized, sequential manner, with competitive enrollment between study sites. Ten (10) study sites will be used in the U.S. and Canada.

[figure not shown]
Diagnostic performance characteristics of F-DCFPyL PET/CT imaging will be evaluated using histopathology as the truth standard. Three independent readers from a central imaging core lab will be given access to F-DCFPyL PET/CT imaging, conventional imaging, and biopsy-guided imaging. The central readers will be blinded to all other clinical information (i.e. pathology data) and radiology assessments. Likewise, local pathologists who generate the histopathology results for the primary endpoint are blinded to all imaging results.

A change in clinical management questionnaire will be filled out by an independent urologist who is not otherwise a participant of the study. To maintain the blind for imaging, a statistician who is independent from the PyL study team will generate subject listings. A combination of imaging and clinical data will then be posted to a share point site where the independent urologist will review these data and fill out the questionnaire based on the results he sees prior to PyL imaging and then again after PyL imaging. To keep things simple, only imaging data from reviewer 1 will be presented for this assessment to be performed.

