## 4.2. Definition of Study Drugs and Treatment Follow-up

All subjects will be administered  $9 \pm 1$  mCi  $(333 \pm 37 \text{ MBq})^{18}\text{F-DCFPyL}$  injection followed by PET/CT imaging and either a biopsy or prostatectomy and lymphadenectomy as illustrated in the white boxes in Figure 1. These are the protocol's planned procedures. If a Physician decides to change these planned procedures after PET/CT imaging is obtained, subjects in Cohort A would not have surgery and subjects in Cohort B would not have a conventional imaging guided biopsy. These changes in planned protocol procedures are listed in the shaded boxes below. This should be a small number of subjects who will not be included in the primary analysis of the primary endpoint or any of the secondary endpoints.

Figure 1: Study Schema

If the subject did not want to go through with this planned procedure or withdrew from the study then this would not constitute a change in planned protocol procedure. If the planned procedure was intended but could not be completed, then this is also not a change in planned procedure.

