#### **5.4.3.** Evaluable Set

*Evaluable subjects* in Cohort A are those who were dosed, had a prostatectomy or lymphadenectomy, and provided a F-DCFPyL PET image result (positive or negative) and a corresponding histopathology result (positive or negative).

Evaluable subjects in Cohort B are those who were dosed, received a conventional image guided biopsy, and provided a F-DCFPyL PET image result (positive or negative) and a corresponding histopathology result (positive for prostate cancer or negative), along with a conventional image that confirms the location of the histopathology sample.

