### 5.5.7.1. Primary Endpoints and Pelvic Lymph Nodes

The primary endpoints of sensitivity and specificity are defined from lymph node imaging results and corresponding pelvic lymph node histology. For an imaging result to be deemed positive for this endpoint, the tissue must have first been removed from that corresponding area. This ensures that an imaging result has the ability to align with the results achieved from pathology. This will be applied to Cohort A subjects only.

PPV and NPV will also be calculated as secondary endpoints from the pelvic lymph nodes. The same definitions used below will apply.

Criteria for Positive PyL Imaging Result	Criteria for Lymph Node Dissection and Positive Histology
If Right or Left Pelvic Lymph Nodes Minimum Template = Positive and  • Tissue was removed from left template and total left nodes removed ≥1 and Template Left Pelvic LN Lesion Count	≥1 positive lymph node on right template if Template Right Pelvic LN Lesion Count from imaging is ≥0 or ≥1 positive lymph nodes on left template if Template Left Pelvic LN Lesion Count from
≥1 or  • Tissue was removed from right template and total right nodes removed ≥1 and Template Right Pelvic LN Lesion Count ≥1  or  Tissue was removed from Pre-sacral nodes and total pre-sacral nodes removed ≥1 and Pre-Sacral Pelvic LN Lesion Count ≥ 1	imaging is ≥0 or ≥1 positive lymph nodes on pre-sacral nodes if Pre-Sacral Pelvic LN Lesion Count from imaging is ≥0 or ≥1positive lymph nodes on other pelvic lymph nodes if Other Pelvic Lymph Node Count from imaging is ≥0
or Tissue was removed from Other lymph nodes and Total nodes removed >=1 and Other Pelvic LN Lesion Count ≥ 1 or	

If tissue was removed from right template and total right nodes removed ≥1 and resection included tissue along the external iliac artery and Right pelvic lymph node external iliac artery= positive or

If tissue was removed from left template and total left nodes removed ≥1 and resection included tissue along the external iliac artery and left pelvic lymph node external iliac artery= positive or

If tissue was removed from right template and total right nodes removed ≥1 and resection included tissue along the common iliac vein and Right pelvic lymph node common iliac vein= positive or

If tissue was removed from left template and total left nodes removed ≥1 and resection included tissue along the common iliac vein and left pelvic lymph node common iliac vein=positive or

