If tissue was removed from right template and total right nodes removed ≥1 and resection included tissue along the common iliac artery and Right pelvic lymph node common iliac artery= positive or

If tissue was removed from left template and total left nodes removed ≥1 and resection included tissue along the common iliac artery and left pelvic lymph node common iliac artery= positive

If Template Right Pelvic LN Lesion Count from imaging is  $\geq 0$  and Total number of positive lymph nodes from Right Template  $\geq 1$  or

If Template Left Pelvic LN Lesion Count from imaging is  $\geq 0$  and Total number of positive lymph nodes from Left Template  $\geq 1$ 

If any of the above criteria are met for imaging then PyL Imaging Result=Positive. If Cohort =A and lymphadenectomy was performed, and lesion counts from imaging results are available for at least one location (right, left, pre-sacral or other) but the above criteria are not met for imaging, then PyL Imaging Results = Negative.

If the above criteria for histology are met then Histology is positive. If all available positive lymph nodes=0 where the corresponding lesion count from imaging≥0 then Histology is negative.

If the lesion counts from all 4 locations (right, left, pre-sacral, and other lymph nodes) are not evaluable on imaging or tissue is not removed from all 4 locations then this endpoint will be missing.

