#### 5.5.8. Lesions Per Subject

The number of lesions detected on imaging categorized as bone, lymph nodes, soft tissue, and the prostate gland will be determined by each of the central imaging core lab independent readers. The sum of lesions per subject per tissue type and overall will be computed for each subject based on each reader's lesion count. This will be calculated from the F-DCFPyL PET/CT scan results as well as the conventional imaging results.

Bone	Soft Tissue	Lymph nodes	Prostate Gland
BN Skull	ST Brain	LN Cervical	ST Prostate Gland Left
BN Thorax	ST Neck	LN Supraclavicular	ST Prostate Gland Right
BN Spine	ST Lungs	LN Axillary	
BN Pelvis	ST Esophageal	LN Mediastinal	
BN Extremities	ST Liver	LN Hilar	
	ST Gall Bladder	LN Mesenteric	
	ST Spleen	LN Elbow	
	ST Pancreas	LN Popliteal	
	ST Adrenal	LN Peri-aortic/para-aortic	
	ST Kidney	LN Other, Non-Pelvic	
	ST Bladder	PLN Template Right	
	ST Prostate Bed	PLN Template Left	
	ST Seminal Vesicle	PLN Pre-Sacral	
	ST Skin	PLN Other, Pelvic	
	ST Muscle		
	ST Other		

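### SAP 4.1 and 4.2 let a PET-based change of plan remove Cohort A subjects from both co-primaries, and no pre-specified analysis bounds the effect

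*SAP*

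**What the plan says.** SAP 4.1: "The physician has the option to change the planned protocol specified procedure", on the basis of the study scan. Of those subjects it says that "these subjects obviating the planned procedure will not be included in any of the primary or secondary endpoints". SAP 4.2 repeats the exclusion and gives an expectation but no figure or cap: "This should be a small number of subjects who will not be included in the primary analysis of the primary endpoint". It also keeps other losses outside this category. A subject who declined the procedure or "withdrew from the study then this would not constitute a change in planned protocol procedure", and a procedure that was intended but not completed is treated the same way.

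The evaluable set requires histology. Protocol 12.2.3 asks for a prostatectomy histopathology result, and SAP 5.4.3 admits a Cohort A subject who "had a prostatectomy or lymphadenectomy, and provided a" PET result with matching histology. SAP 5.6.1 imputes nothing.

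For the co-primaries, SAP 5.5.7.1 ties the PET result itself to surgery: "For an imaging result to be deemed positive for this endpoint, the tissue must have first been removed from that corresponding area". A negative result is assigned only if the subject is in Cohort A "and lymphadenectomy was performed, and lesion counts from imaging results are available for at least one location". With no tissue removed, the endpoint is missing.

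SAP 5.5.8 has no such condition: "The number of lesions detected on imaging categorized as bone, lymph nodes, soft tissue, and the prostate gland will be determined by each" (the sentence then names the core lab's readers). It lists four pelvic-node locations (template right, template left, pre-sacral, other pelvic).

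**The concern.** When the index test influences who receives the reference standard, sensitivity and specificity estimated from verified subjects alone can be biased (partial verification). Diverting pelvic PET-positives removes true and false positives, which raises observed specificity and lowers observed sensitivity. Diverting pelvic PET-negatives, for example because of a PET finding elsewhere, does the reverse.

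Nothing planned addresses this. The per protocol analysis (SAP 7.6.1) and the any-two-readers analysis (SAP 7.6.2) use the evaluable set or a subset of it. The exploratory PPV for changed-plan subjects (SAP 5.5.7.4 and 7.8) needs tissue, pools the cohorts, and gives neither sensitivity nor specificity. The 10% allowance in SAP 4.3 protects the number of evaluable subjects but does not deal with loss that depends on the PET result. Because the SAP 5.5.7.1 variable is undefined for an unoperated subject, adding the words worst-case analysis to the SAP would not be enough. The PET result to be used for those subjects must also be defined.

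**Working it through.** **Inputs from SAP 4.3 and 7.6.1.** Prevalence 0.20; sensitivity (Se) 0.40 versus 0.60; specificity (Sp) 0.80 versus 0.878; two-sided 5%, 80% power; 236 evaluable, 262 dosed; success when the normal-approximation 95% lower limit exceeds 0.80 (Sp) and 0.40 (Se). Every diversion rate below is an assumption.

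**The plan's own figure.** The SAP formula gives 47.09 positives for sensitivity, and 47.09/0.20 = 235.5, so 236. Specificity needs 184.5 negatives, and 184.5/0.80 = 230.6, so 231. The larger governs, and 236/0.9 = 262.2, stated as 262. The sample size reproduces.

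**Shift in the estimates.** Let rt and rf be the shares of true and false positives diverted.

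- Observed Sp = Sp/(Sp + (1−rf)(1−Sp))
- Observed Se = (1−rt)Se/((1−rt)Se + 1−Se)

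With rt = rf = 20%: Sp = 0.878/(0.878 + 0.8×0.122) = 0.900 and Se = 0.48/(0.48 + 0.40) = 0.545. Expected PET-positives are 262×(0.20×0.60 + 0.80×0.122) = 57.

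**Chance that one reader passes both tests.** This is the exact binomial probability that each lower limit clears its threshold, averaged over the number of positives (binomial, 262, 0.20) and the numbers verified, with no other loss.

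| PET-positives diverted | Subjects | Observed Sp | Observed Se | Both pass |
|---|---|---|---|---|
| 0% | 0 | 0.878 | 0.600 | 74% |
| 10% | 6 | 0.889 | 0.574 | 66% |
| 20% | 11 | 0.900 | 0.545 | 50% |
| 30% | 17 | 0.911 | 0.512 | 31% |

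At true Sp 0.80 and Se 0.60 the same calculation gives a false pass of 3.0, 7.6, 13.9 and 16.4%. With rf a quarter of rt it is 3.0, 3.3, 3.3 and 2.7%.

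In the other direction, diverting 10% of PET-negatives gives Sp = 0.9×0.878/(0.9×0.878 + 0.122) = 0.866 and Se = 0.60/(0.60 + 0.9×0.40) = 0.625.

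**What bounds would show.** Take 262 subjects with TP 31, FN 21, FP 26, TN 184.

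- Six PET-positives diverted (3 TP, 3 FP): observed Se 28/49 = 0.571 (lower limit 0.433) and Sp 184/207 = 0.889. Bounds: Se 28/49 to 34/55 = 0.571 to 0.618; Sp 184/213 to 184/207 = 0.864 to 0.889. Both tests pass throughout.
- Eleven diverted (6 TP, 5 FP): observed Se 25/46 = 0.543, lower limit 0.3995, a fail. With one fewer true positive lost, 26/47 has lower limit 0.411, a pass. Bounds: Se 25/46 to 36/57 = 0.543 to 0.632; Sp 184/216 to 184/205 = 0.852 to 0.898.
- Ten PET-negatives diverted (1 FN, 9 TN): Se bounds 31/61 to 31/51 = 0.508 to 0.608; the worst-case lower limit is 0.383.

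**How few subjects matter in the extreme case.** At 236 evaluable (28/47 and 166/189), adding 7 excluded subjects all as false positives gives 166/196, lower limit 0.7965. Adding 6 all as false negatives gives 28/53, lower limit 0.394. Either reverses a success, with 6/262 = 2.3% or 7/262 = 2.7% of those dosed. It requires PET to be wrong in every one of them.

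**The case against.** The exclusion is pre-specified and disclosed. The changed-plan set is defined (SAP 5.4.4), and the SAP expects it to be small. Table 4 in SAP 12.1 lists imaging, histology and procedure summaries on the Safety Set (14.2.3-11 to -13) and a listing of subjects excluded from the Evaluable Set (16.2.3-1). No document gives a diversion rate or says which PET finding would trigger a change. All of this stands and limits the point. Even so, no listed title crosses the pelvic-node PET result with verification status (the table shells are not available), and any bound assembled later would be post hoc.

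Stronger readings that a reader might infer are not supported:

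- **That unoperated subjects have no PET data.** Only the SAP 5.5.7.1 variable is undefined for them. The SAP 5.5.8 counts are not conditional on surgery, and SAP 5.5.7.4 defines a PET-positive rule for changed-plan Cohort A subjects. A crude worst case needs only the number excluded.
- **That both co-primaries are inflated.** Losing PET-positives lowers sensitivity, and losing PET-negatives lowers specificity. Where plausible rates hurt at all, the likelier harm is to sensitivity and the chance of success. A materially higher false-pass chance needs true specificity near 0.80 and false positives diverted about as often as true ones.
- **That the percentages describe the trial's decision rule.** They are for one reader. The same-two-of-three-readers rule in SAP 7.6.1 depends on inter-reader correlation, which the documents do not give.
- **That a failed bound would show verification bias.** Ordinary attrition can fail it alone. Suppose no PET-based diversion, and the planned 26 losses (262 − 236) split as 6 PET-positive and 20 PET-negative (assumed). Worst-case sensitivity is then 28/(28+19+20) = 28/67 = 0.418, lower limit 0.300.

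**Conclusion.** The concern holds in a limited form. Verification in Cohort A can depend on the PET scan, those subjects leave both co-primaries, and the SAP pre-specifies nothing that shows how far either estimate could move as a result. This is a gap in planned analysis, not in data collection, and it does not show that the primary result would be wrong. If no plans are changed because of PET, the effect is nil. At an assumed 10% diversion of PET-positives, observed specificity rises by about 0.01 and sensitivity falls by about 0.03, and the single-reader chance of joint success drops from 74% to 66%. At 30% it is 31%. These figures rest on the planning values in SAP 4.3, on diversion driven by pelvic-node positivity, and on no other loss. It is worth correcting because it is cheap and would let the report answer an obvious question about robustness.

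**What to change.** Leave the primary analysis unchanged and add three items to the SAP.

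1. **PET result for unverified dosed Cohort A subjects only.** Per reader, use the four pelvic counts in SAP 5.5.8: positive if any is at least 1, negative if all evaluable counts are 0, missing if none is evaluable. Verified subjects keep their SAP 5.5.7.1 classification. Re-scoring them on counts would penalise PET nodes in unresected areas, which Protocol 12.3.1 leaves out of the tabulation. If 10 of 184 true negatives had such a node (assumed), specificity would read 174/210 = 0.829, lower limit 0.778, a fail caused only by the change of variable.
2. **Verification table.** Per reader, show verified and unverified subjects by PET result, with the unverified split into PET-based change of procedure and other reasons.
3. **Bounds in SAP 7.6.2.** With m+ and m− unverified PET-positives and PET-negatives, Se runs from TP/(TP+FN+m−) to (TP+m+)/(TP+m++FN), and Sp from TN/(TN+FP+m+) to (TN+m−)/(TN+m−+FP). Calculate them first with m+ and m− limited to PET-based changes of procedure, then separately for all unverified subjects. Label the second set as also including ordinary attrition, and state that neither set is a success criterion.

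The cost is some SAP wording, one derived variable, one table and closed-form arithmetic on data already collected. The supporting figures may look less favourable. A count-based positive in an unverified subject may also lie where surgery would not have removed tissue, so that result should be read as an approximation.

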## 4.2. Definition of Study Drugs and Treatment Follow-up

All subjects will be administered  $9 \pm 1$  mCi  $(333 \pm 37 \text{ MBq})^{18}\text{F-DCFPyL}$  injection followed by PET/CT imaging and either a biopsy or prostatectomy and lymphadenectomy as illustrated in the white boxes in Figure 1. These are the protocol's planned procedures. If a Physician decides to change these planned procedures after PET/CT imaging is obtained, subjects in Cohort A would not have surgery and subjects in Cohort B would not have a conventional imaging guided biopsy. These changes in planned protocol procedures are listed in the shaded boxes below. This should be a small number of subjects who will not be included in the primary analysis of the primary endpoint or any of the secondary endpoints.

Figure 1: Study Schema

If the subject did not want to go through with this planned procedure or withdrew from the study then this would not constitute a change in planned protocol procedure. If the planned procedure was intended but could not be completed, then this is also not a change in planned procedure.

## 4.3. Sample Size

The primary analysis in Cohort A will test the co-primary endpoints of sensitivity and specificity of F-DCFPyL PET imaging relative to histopathology for the evaluable set of subjects in Cohort A with metastatic disease. For each co-primary endpoint, there will be three independent imaging readers. At least two of the three readers must reject the null hypothesis for specificity to be deemed a success. If specificity is a success, then the same two readers need to reject the null hypothesis for sensitivity leading to overall success of the primary endpoint. The null hypotheses will be tested in the following order:

- 1. Specificity of F-DCFPyL PET imaging relative to histopathology in Cohort A  $H_0$ :  $\pi_{Sp} = 0.80$  versus  $H_1$ :  $\pi_{Sp} \neq 0.80$
- 2. Sensitivity of F-DCFPyL PET/CT imaging relative to histopathology in Cohort A  $H_{01}$ :  $\pi_{Se} = 0.40$  versus  $H_{11}$ :  $\pi_{Se} \neq 0.40$

where  $\pi_{Se}$  is the true sensitivity and  $\pi_{Sp}$  is the true specificity of F-DCFPyL PET imaging.

A total of 262 subjects from Cohort A will provide 80% power to reject the null hypothesis about sensitivity at the 5% significance level if the true sensitivity is at least 60% and at least 80% power to reject the null hypothesis about specificity at the 5% significance level if the true specificity is at least 87.8%. These calculations are based on the following assumptions:

• the probability of a positive histopathology sample in Cohort A is 20%,

The sample size is based on the normal approximation to the binomial distribution without a continuity correction.

$$n \ge \left\{ \frac{z_{\alpha/2} \sqrt{P_0(1 - P_0)} + z_{\beta} \sqrt{P_1(1 - P_1)}}{P_1 - P_0} \right\}^2$$

where P0 are P1 are values of sensitivity under the null and alternative hypotheses, respectively. After adjusting sensitivity and specificity separately by their corresponding prevalence values, a total in 236 subjects are needed. Assuming a 10% drop out or non-evaluable rate increases the required number of subjects in Cohort A to 262.

The type I error rate will be preserved at 5% by requiring that both null hypotheses be rejected to draw the conclusion that F-DCFPyL is efficacious for imaging. The second primary endpoint is only tested if the first primary endpoint is rejected at the 0.05 level of significance per a fixed sequential method. If the first hypothesis fails to be rejected, no further testing will be conducted.

No formal power calculations will be performed for Cohort B since it is not a primary endpoint. Approximately 115 subjects will be dosed in this cohort.

#### 4.4. Randomization

This study is not randomized. One treatment will be administered.

#### 4.5. Clinical Assessments

See Table 2 for the schedule of study assessments.

**Table 2: Schedule of Assessments** 

	Screening/ Baseline	 F-DCFPyL Dosing	 F-DCFPyL Imaging	Pre-Surgery/ Biopsy Follow-Up
	Day -30 to Day 1	Day 1	1-2 Hours Post-Dosing	Within 28 Days Post- Dosing
Cohorts A and B				
Informed Consent & Eligibility	X			
Demographics (date of birth, race, ethnicity, height, weight)	X			
Medical History	X			
Prior Cancer Medications & Treatments	X			
Clinical Labs (hematology, chemistry)	X 			X
PSA (total) & Testosterone	X 			
Vital Signs (blood pressure, heart rate, temperature, respiratory rate)	X	X (pre-dosing)	X (pre-imaging)	X
12-Lead ECG		X (pre-dosing)	X (pre-imaging)	
 F-DCFPyL Administration		X		
Whole Body PET/CT			X	

**Table 2: Schedule of Assessments** 

	Screening/ Baseline	 F-DCFPyL Dosing	 F-DCFPyL Imaging	Pre-Surgery/ Biopsy Follow-Up	
	Day -30 to Day 1	Day 1	1-2 Hours Post-Dosing	Within 28 Days Post- Dosing	
Adverse Events		2	X	X 	
Concomitant Medications	X	X		X	
Conventional Imaging (CT or MRI, bone scan)	X 				
Surgery or Image-Guided Biopsy				X 	
Subset of Cohort A or B at Johns Hopkins Universi	Subset of Cohort A or B at Johns Hopkins University only for PK Analysis				
Blood Collection		X  (9 collections)			
Urine Collection		X  (3 collections)			
Whole Body PET/CT			X  (3 scans)		

 To be collected prior to dosing, if collected on day of dosing. If PSA and testosterone have not been tested within 30 days of study drug injection, a blood draw will be collected prior to dosing.

- 3 Surgery or biopsy to occur at least 12 hours from time of F-DCFPyL dosing but not more than 28 days from dosing. In Cohort B, imaging used to guide biopsy (i.e., CT, MRI) will be submitted to a central core imaging lab.
- 4 Analysis should occur immediately following last sample collected.
- 5 A safety phone call will also occur  $7(\pm 3)$  days post dosing [if surgery, biopsy or a change in planned protocol procedure has not yet occurred] and  $21(\pm 7)$  days post biopsy for just the subjects who had a conventional image guided biopsy in Cohort B.
-  If a subject's planned procedure (RP or biopsy) for prostate cancer changes following F-DCFPyL imaging, the alternate or additional prostate cancer procedure and corresponding histopathology data will be recorded in the electronic case report form (eCRF).

